### **1.4 Exploratory Objectives**

#### Exploratory safety objectives

- 1.4.1 To evaluate the short term, 6-month, and 12-month safety and tolerability of atezolizumab in combination with stereotactic radiation in patients with TNBC and brain metastases.

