## **5.6 Duration of Follow Up**

Participants removed from protocol therapy for unacceptable adverse event(s) will be followed until resolution or stabilization of the adverse event. Participants who are taken off protocol therapy for extracranial progression in the setting of intracranial response or stable disease will be followed for CNS progression and survival after removal from protocol therapy. It is understood that it may not always be feasible for patients to return for restaging evaluation after coming off protocol therapy, though a strong effort should be made to encourage restaging every 6-12 weeks. In this specific setting, lack of restaging scans at the interval will not

constitute a protocol deviation or violation. Participants who are removed from protocol therapy for intracranial disease progression will be followed for survival until death.

Participants who are removed from protocol therapy before the 6-month post-radiation follow-up visit will be contacted by phone by a member of the study team to be assessed for possible latent radiation toxicities.

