#### Adverse Events

An AE is any unfavorable and unintended sign, symptom, or disease temporally associated with the use of an investigational medicinal product (IMP) or other protocol-imposed intervention, regardless of attribution.

This includes the following:

- AEs not previously observed in the patient that emerge during the protocol-specified AE reporting period, including signs or symptoms that were not present prior to the AE reporting period
- Complications that occur as a result of protocol-mandated interventions (e.g., invasive procedures such as cardiac catheterizations).
- If applicable, AEs that occur prior to assignment of study treatment associated with medication washout, no treatment run-in, or other protocol-mandated intervention.
- Preexisting medical conditions (other than the condition being studied) judged by the investigator to have worsened in severity or frequency or changed in character during the protocol-specified AE reporting period.
- 

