### **7.2.1 Adverse Event Reporting Period**

The study period during which all AEs and SAEs must be reported begins after informed consent is obtained- and initiation of study treatment and ends 30 days following the last administration of study treatment or study discontinuation/termination, whichever is earlier. After this period, investigators should only report SAEs that are attributed to prior study treatment.

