### **7.2.2 Assessment of Adverse Events**

All AEs and SAEs whether volunteered by the subject, discovered by study personnel during questioning, or detected through physical examination, laboratory test, or other means will be reported appropriately. Each reported AE or SAE will be described by its duration (i.e., start and end dates), regulatory seriousness criteria if applicable, suspected relationship to the atezolizumab (see following guidance), and actions taken.

To ensure consistency of AE and SAE causality assessments, investigators should apply the following general guideline:

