### 13.2 Sample Size, Accrual Rate and Study Duration

The primary endpoint is bi-compartmental PFS according to RANO-BM criteria. A sample size of 45 was chosen to achieve 80 % power to detect a difference between the null hypothesis median PFS of 2 months and alternative of 3.5 months at a one-sided type I error of 0.05.

The null hypothesis was derived from two sources: First, a prospective trial testing the combination of irinotecan and iniparib in patients with metastatic triple-negative breast cancer and new/progressive brain metastases reported a median time to progression (which included both intracranial and extracranial progression) of 2.14 months [Anders *et al.*, 2014]. Next, in a retrospective study describing outcomes of breast cancer patients after initial stereotactic radiation, time to intracranial progression was significantly shorter in patients with triple-negative breast cancer, relative to the luminal A subtype (HR 28.0 in multivariable model,  $p=0.003$  [Dyer *et al.*, 2012]. Although the numbers are small, the point estimate for the time to intracranial progression in the triple-negative subset was 2.5 months [Dyer *et al.*, 2012].

Anticipated accrual of approximately 2 patients per month, it will require approximately 24 months of patient accession to reach 45 patients. The primary analysis of PFS and OS will be

time-driven and performed after 6 months of additional follow-up.

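### General AE collection stops 30 days after the last dose, so the 6- and 12-month safety objective is supported only for radiation toxicity and attributed SAEs

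*Combined protocol and SAP*

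**What the plan says.** Section 1.4.1 states the exploratory safety objective: "To evaluate the short term, 6-month, and 12-month safety and tolerability of atezolizumab in combination with stereotactic radiation". It is not limited to radiation effects.

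Section 7.2.1 says that the period for reporting all AEs and SAEs "ends 30 days following the last administration of study treatment or study discontinuation/termination, whichever is earlier". It continues: "After this period, investigators should only report SAEs that are attributed to prior study treatment". The study calendar (section 10) agrees: AE evaluation is marked from screening to the off-treatment visit and is blank under follow-up. Section 13.7 summarizes toxicity by maximum grade and gives no 6- or 12-month window, denominator or handling of early exit.

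Radiation toxicity has a separate track. Section 5.2.4.1.8 schedules necrosis assessments at about 6 months (window 5 to 8) and, where feasible, about 12 months (window 11 to 14). Under section 5.6, patients off therapy before the 6-month visit "will be contacted by phone by a member of the study team to be assessed for possible latent radiation toxicities". Section 13.4 sets stopping boundaries for symptomatic necrosis at 6 months and 1 year.

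Two related passages matter. Section 7.2.2 describes each event by its "suspected relationship to the atezolizumab (see following guidance), and actions taken", without naming radiation. Section 7.1.2 counts as AEs, where applicable, "AEs that occur prior to assignment of study treatment associated with medication washout, no treatment run-in, or other protocol-mandated intervention", whereas 7.2.1 opens reporting after consent and the start of treatment.

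**The concern.** The objective and the collection rule run on different clocks. The objective is fixed in calendar time; collection is tied to the last dose. In a population with short expected PFS, many patients will be off drug well before month 6.

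A patient who develops, say, non-serious colitis two months after the last dose and is managed as an outpatient falls outside 7.2.1. Sections 7.1.3.1 and 7.5 make colitis reportable as an event of special interest whether serious or not, and state no end date. A site cannot tell which rule governs.

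Patients leave collection because of progression, toxicity or death, so exit is informative. Those still observed at months 6 and 12 are mainly those doing best on treatment. A table of overall AEs at those times would make late non-serious toxicity look rare partly because nobody was asked to record it.

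**Working it through.** **Inputs.** N = 45 and PFS medians of 2 months (null) and 3.5 months (alternative), section 13.2; OS medians of 5 and 10 months, section 13.6.2; collection ends 30 days = 0.99 months after the last dose, section 7.2.1. Time on treatment is not stated. I assume that time to last dose is exponential with the design PFS median, then vary this.

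**The plan's own figure first.** Section 13.2 says "A sample size of 45 was chosen to achieve 80 % power", for a "null hypothesis median PFS of 2 months and alternative of 3.5 months". With exponential PFS and a Brookmeyer-Crowley-type test at 2 months:
- S1 = 0.5^(2/3.5) = 0.673; SE = sqrt(0.673 × 0.327 / 45) = 0.0699
- power = Φ((0.673 − 0.5)/0.0699 − 1.645) = 79.6%

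This reproduces the stated 80% with exponential PFS. It says nothing about time on treatment.

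**Share in general AE collection at month t** = 0.5^((t − 0.99)/m). **Share alive** = 0.5^(t/median OS). **Share of those alive who are outside collection** = 1 − (in collection)/(alive).

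| Medians (PFS, OS) | Month | In collection | Alive | Alive but outside |
|---|---|---|---|---|
| 2, 5 (null) | 6 | 17.6% (8 of 45) | 43.5% (20) | 60% |
| 3.5, 10 (alternative) | 6 | 37.0% (17) | 66.0% (30) | 44% |
| 2, 5 (null) | 12 | 2.2% (1) | 18.9% (8-9) | 88% |
| 3.5, 10 (alternative) | 12 | 11.3% (5) | 43.5% (20) | 74% |

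The last column treats everyone in collection as alive, so it is if anything slightly low.

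**Cross-paired medians.** PFS 3.5 with OS 5: 1 − 0.370/0.435 = 15% at month 6 and 1 − 0.113/0.189 = 40% at month 12. PFS 2 with OS 10: 1 − 0.176/0.660 = 73% and 1 − 0.022/0.435 = 95%.

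**Treatment past progression.** Section 5.5 allows treatment until progression by the immune criteria, and section 11.4.2 allows up to 3 months (13 weeks) for confirmation. Section 1.1.1 instead ends treatment at RANO-BM or RECIST progression; the two must be reconciled. With 3-weekly doses, the window is open at month 6 (26.1 weeks) only if the last dose is at week 24 or later, and at month 12 (52.2 weeks) only if it is at week 48 or later. One month is 4.348 weeks, so a 3.5-month median is 15.2 weeks and a 2-month median is 8.7 weeks.

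If every patient uses all 13 weeks:
- Month 6 requires progression after week 24 − 13 = 11, or after week 6 if progression is detected only at the next scheduled scan (week 12). PFS 3.5: 0.5^(11/15.2) = 61% to 0.5^(6/15.2) = 76%. PFS 2: 42% to 62%.
- Month 12 requires progression after week 35, or after week 33 with scheduled detection. PFS 3.5: 20% to 22%. PFS 2: 6% to 7%.

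This is an upper bound: 76% exceeds the 66% expected to be alive. With 4 to 6 weeks of continuation and PFS 3.5, 40% to 44% remain at month 6.

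**Break-even.** Half of all patients remain in collection only if median time to last dose is at least 5.0 months (month 6) or 11.0 months (month 12).

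**The case against.** A reader might infer that the 6- and 12-month objective cannot be answered at all. The documents do not support that. Delayed radiation toxicity is assessed at both time points whether or not the patient is on drug (5.2.4.1.8), with stopping boundaries (13.4) and a planned cumulative incidence of necrosis (13.7). SAEs attributed to treatment stay reportable without a time limit (7.2.1, 7.3.2.6), which covers many severe late events. An AE that leads to removal from therapy is followed to resolution or stabilization (5.6).

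Other strong readings also fail:
- **No remote contact at 12 months.** Section 5.2.4.1.8 permits local imaging and telephone assessment for patients who cannot travel, without limiting this to month 6. Only sections 5.6 and 13.4 confine the off-therapy telephone contact to the 6-month visit.
- **Causality ignores radiation throughout.** Section 7.1.3 grades attribution to study treatment, and section 5.4 names radiation for dose-limiting toxicity. Only 7.2.2 is narrower.
- **Most 6-month survivors are outside collection.** The matched-median range of 44-60% straddles one half, and the gap can nearly close if treatment runs long past progression.
- **Pre-treatment events are never collected.** The calendar marks AE evaluation at screening, and CSF collection is optional. The start-date wording is unclear; it is not a proven exclusion.

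It can also be said that how long to collect non-serious AEs is a design choice, and that the objective is exploratory. Both are true. But having stated the objective, the plan needs either data for it or narrower wording. The radiation contacts are framed for necrosis or latent radiation toxicity, so they do not by themselves supply the missing AEs.

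**Conclusion.** The point holds in a limited form. The late safety objective is supported for radiation necrosis, latent radiation toxicity and attributed SAEs. It is not supported for other AEs, chiefly non-serious immune-related events, and section 13.7 has no time-specific summary that would reveal the gap.

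On the design medians, 63-82% of enrolled patients have left general collection by month 6 and 89-98% by month 12. Some of those exits are deaths, which longer collection would not recover, so the share outside among patients alive is the fairer measure. The month-12 gap persists under matched medians even at the 13-week bound: 1 − 0.222/0.435 = 49% to 1 − 0.061/0.189 = 68% of those alive would still be outside. The month-6 gap is uncertain.

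The sizes rest on exponential times and on equating time to last dose with PFS. The direction of the bias rests only on the fact that patients leave collection through progression or toxicity. The primary and key secondary efficacy analyses are unaffected.

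**What to change.** - Amend 7.2.1 so that Grade 2 or higher AEs at least possibly related to atezolizumab or stereotactic radiation, serious or not, are recorded through the existing 6- and 12-month contacts. Grade 2 is already the routine threshold in 7.9.
- State in 5.6 that the telephone contact for off-therapy patients also applies at 12 months.
- Align causality in 7.2.2 with 7.1.3 and 5.4 so that radiation is included.
- In 13.7, report 6- and 12-month figures with the number alive and contacted as denominator.
- State whether the special-interest rule (7.1.3.1, 7.5) continues after the 30-day window.
- Reconcile the start of AE reporting across 7.1.2, 7.2.1 and the calendar, so that complications of protocol-mandated baseline procedures are captured from consent.

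The cost is protocol wording and a short AE form at contacts that already exist. The downside is some extra data entry and less complete data by telephone than at visits. If this is not adopted, limit the 6- and 12-month part of objective 1.4.1 to radiation necrosis and attributed SAEs.

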### **7.2.2 Assessment of Adverse Events**

All AEs and SAEs whether volunteered by the subject, discovered by study personnel during questioning, or detected through physical examination, laboratory test, or other means will be reported appropriately. Each reported AE or SAE will be described by its duration (i.e., start and end dates), regulatory seriousness criteria if applicable, suspected relationship to the atezolizumab (see following guidance), and actions taken.

To ensure consistency of AE and SAE causality assessments, investigators should apply the following general guideline:

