#### 5.4 Definition of Dose-Limiting Toxicity

Dose-limiting toxicity is defined as any of the following events occurring from first dose of Atezolizumab until Cycle 3 Day 1 if judged by the investigator to be possibly, probably, or definitely related to study drug and/or radiation administration:

- Death
  - $\geq$  Grade 3 treatment-emergent neurological toxicity
  - Asymptomatic grade 4 hematologic toxicity lasting  $\geq 14$  days unless deemed by the investigator to be clinically insignificant
  - $\geq$  Grade 4 thrombocytopenia of any duration
  - $\geq$  Grade 3 Febrile neutropenia
  - $\geq$  Grade 3 Thrombocytopenia if associated with bleeding
  - $\geq$  Grade 3 elevation in AST or ALT associated with a grade 2 elevation in bilirubin that is at least possibly related to study drug (Hy's Law)
  - $\geq$  Grade 3 non-hematologic laboratory value if:
    - Medical intervention is required to treat the patient, or
    - The abnormality leads to hospitalization, or
    - The abnormality persists  $> 7$  days
- Excluding:
- Alkaline phosphatase  $\leq 10.0$ x ULN in a patient with  $\geq$  grade 2 alkaline phosphatase elevation at baseline as a result of bone metastasis
  - Any laboratory values deemed by the investigator to be clinically insignificant
- $\geq$  Grade 3 pneumonitis of any duration
  - $\geq$  Grade 3 Fatigue lasting  $> 5$  days
  - $\geq$  Grade 3 other non-laboratory toxicity lasting  $> 3$  days despite optimal supportive care, excluding Alopecia (of any grade).

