#### Yes

There is a plausible temporal relationship between the onset of the AE and administration of atezolizumab, and the AE cannot be readily explained by the subject's clinical state, intercurrent illness, or concomitant therapies; and/or the AE follows a known pattern of response to atezolizumab; and/or the AE abates or resolves upon discontinuation of atezolizumab or dose reduction and, if applicable, reappears upon re-challenge.

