## No

Evidence exists that the AE has an etiology other than atezolizumab (e.g., preexisting medical condition, underlying disease, intercurrent illness, or concomitant medication); and/or the AE has no plausible temporal relationship to atezolizumab administration (e.g., cancer diagnosed 2 days after first dose of study drug).

Expected adverse events are those adverse events that are listed or characterized in the Package Insert (P.I) or current Investigator Brochure (I.B).

Unexpected adverse events are those not listed in the P.I or current I.B or not identified. This includes adverse events for which the specificity or severity is not consistent with the description in the P.I. or I.B. For example, under this definition, hepatic necrosis would be unexpected if the P.I. or I.B. only referred to elevated hepatic enzymes or hepatitis.

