#### 7.3.2.6 Post-Study Adverse Events

The investigator should expeditiously report any SAE occurring after a subject has completed or discontinued study participation if attributed to prior study drug exposure. If the investigator should become aware of the development of cancer or a congenital anomaly in a subsequently conceived offspring of a female subject who participated in the study, this should be reported as an SAE.

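### Section 7.2.2 judges causality against atezolizumab alone, so a radiation-caused event can be coded unrelated and a late radiation SAE other than necrosis may go unreported

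*Combined protocol and SAP*

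**What the plan says.** The combined protocol and SAP sets out causality in several places, with different targets.

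- **Section 7.2.2** describes each AE and SAE by, among other things, its "suspected relationship to the atezolizumab (see following guidance), and actions taken". One limb of the Yes rule needs plausible timing after atezolizumab and an event that "cannot be readily explained by the subject's clinical state, intercurrent illness, or concomitant therapies". The No rule begins: "Evidence exists that the AE has an etiology other than atezolizumab". Radiation is not mentioned as a possible cause to be recorded.
- **Section 7.1.3** gives a five-level scale, from definite to unrelated, against *study treatment*.
- **Section 5.4** counts a DLT if the investigator judges it "possibly, probably, or definitely related to study drug and/or radiation administration".
- **Section 7.2.1** requires all AEs and SAEs during a period that "ends 30 days following the last administration of study treatment or study discontinuation/termination, whichever is earlier". It continues: "After this period, investigators should only report SAEs that are attributed to prior study treatment".
- **Section 7.3.2.6**, for subjects who have completed or left the study, asks for expedited reporting of an SAE "if attributed to prior study drug exposure".

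*Study treatment* is not defined. Objective 1.4.15 uses it for the combination; Section 6.1.1 uses it for atezolizumab infusions that may be suspended.

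**The concern.** The intervention is a combination, and objective 1.4.1 is its short-term, 6-month and 12-month safety. If the only guideline offered for consistent causality assessment looks at one component, harm from the other component is recorded as unrelated.

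Two things depend on attribution. The first is the DLT judgment: three or more DLTs in the first six patients close enrollment (Section 13.4). The second is SAE reporting after the 30-day window, which Section 7.2.1 makes conditional on attribution. Delayed radiation toxicity is looked for in that later period, with radiation visits at 5 to 8 and 11 to 14 months (Section 5.2.4.1.8).

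**Working it through.** The point rests on wording, so the plan has no figure of its own to reproduce. I traced one kind of event through each rule: an SAE clearly due to stereotactic radiation but not necrosis, such as a seizure or edema.

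**Step 1. Is the event related?**

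| Section | Target | Result |
|---|---|---|
| 5.4 | Drug and/or radiation | Related |
| 7.1.3 | *Study treatment* | Related only if the term includes radiation |
| 7.2.2 | Atezolizumab | No, where radiation is the evident cause |

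The limbs of the 7.2.2 Yes rule are joined by and/or, so an investigator who suspects a joint effect could still answer Yes. The correct statement is that the event *can* be coded No. No section says which scale governs, although 7.2.2 offers its guideline as the means of keeping causality assessments consistent.

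**Step 2. Does the record support the DLT count?** Section 5.4 uses the words possibly, probably and definitely, which are levels of the 7.1.3 scale, and the investigator makes that judgment directly. A Yes/No answer about atezolizumab cannot confirm or contradict a judgment about radiation. As a side check, the run-in table in 13.4 is correct as printed: P(at most 2 DLTs in 6) at true rates 0.1 to 0.7 is 98.4, 90.1, 74.4, 54.4, 34.4, 17.9 and 7.0%, against 98, 90, 74, 54, 34, 18 and 7% stated. The arithmetic of the rule is not at issue; the audit trail for its input is.

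**Step 3. Inside the reporting window.** Section 7.2.1 requires all AEs and SAEs, 7.4 requires SAEs without an attribution condition, 7.5 requires SAEs whether or not related to atezolizumab, and 7.9 requires all Grade 2 or higher AEs. The event is reported however it is coded.

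**Step 4. More than 30 days after last treatment, still on study.** Section 7.2.1 now requires the SAE only if it is attributed to *study treatment*. The outcome depends on two unsettled choices:

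| *Study treatment* means | Causality judged by 7.1.3 | Causality judged by 7.2.2 |
|---|---|---|
| Atezolizumab and/or radiation | Reported | Coded No; may not be reported |
| Atezolizumab | Not required | Not required |

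Only one of the four combinations clearly leads to a report.

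**Step 5. After participation ends.** Under Section 5.7 this means loss to follow-up, withdrawal of consent for data submission, death or study closure. Section 7.3.2.6 then refers to drug exposure, which on its plain words leaves radiation out.

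**The case against.** Much of the case on the other side stands.

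- **Sections 7.2.1 and 7.3.2.6 have different triggers.** A reader might infer that they contradict each other for any patient more than 30 days off drug. They do not: 7.2.1 runs from last treatment, and 7.3.2.6 from the end of participation. A patient off atezolizumab at month 5 is normally still on study under 5.6 and 5.7, so 7.2.1 applies. Nor does 7.3.2.6 limit itself to drug-attributed SAEs; it adds a duty.
- **Section 7.2.1 does not name radiation.** A reader might take it as covering radiation. That is an inference from an undefined term.
- **Radiation events are not lost wholesale.** A reader might infer that they go unreported in general. Step 3 rules this out inside the window. Necrosis is adjudicated and has its own stopping boundary. The radiation visits and phone contacts look for delayed radiation toxicity more widely, and 13.4 allows termination if it is judged excessive. These routes elicit events; they do not settle whether a late SAE other than necrosis must be reported as one. Section 7.5 states no end date of its own, but 7.2.1 sets the reporting period and narrows it afterwards.
- **No planned safety table uses attribution.** Section 13.7 summarizes toxicity by maximum grade, and DLTs are judged under 5.4, not derived from 7.2.2.
- **A share of patients cannot be given.** A reader might use the planning PFS medians: 1 − 0.5^(4/3.5) = 54.7% and 1 − 0.5^(4/2) = 75% have an event by month 4, hence would be out of the window at month 5. That counts deaths as patients at risk of a late SAE and assumes dosing stops at progression, whereas Section 5.5 allows treatment to continue until progression by the immune criteria. With exponential OS at the medians in 13.6.2, 0.5^(5/5) = 50% and 0.5^(5/10) = 70.7% are alive at month 5. The share alive and progressed by month 4 is then 0.50 − 0.25 = 25% to 0.50 − 0.177 = 32% under the null medians, or 0.707 − 0.453 = 25% to 0.707 − 0.371 = 34% under the alternatives. Even these figures keep the dosing assumption, and they count patients under the rule, not SAEs missed.

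What remains is more than a request for tidier terms, because post-window SAE reporting turns on attribution and the stated guideline points to No.

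**Conclusion.** The point holds in a bounded form and should be corrected. A radiation-caused event can be coded unrelated under 7.2.2 while counting as related under 5.4; the 7.2.2 record cannot verify the investigator's DLT judgment; and a radiation SAE other than necrosis may not be reported once the patient is more than 30 days past last treatment. The efficacy analyses, in-window safety reporting, maximum-grade tables and necrosis boundaries are untouched.

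I put no number on the SAEs affected. The documents give no rate of late radiation SAEs other than necrosis and no distribution of last-dose times. The conclusion assumes that sites follow the 7.2.2 guideline when they attribute SAEs. The AE form is not in the documents; if it already has a radiation attribution field, the protocol text still needs to be brought into line with it.

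**What to change.** 1. Define *study treatment* once, as atezolizumab and/or stereotactic radiation.
2. In 7.2.2, record relationship to atezolizumab and relationship to stereotactic radiation separately, both on the five-level scale of 7.1.3, so that the DLT relationship under 5.4 can be checked against the two fields.
3. Use the defined term in 7.2.1 and in 7.3.2.6.

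The cost is one extra attribution field on the AE form and brief wording edits. Sample size, visits and planned analyses do not change.
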